3.4.2 Physical examination

The physical examination data will be collected at baseline and at each scheduled visit after baseline, and the results will be evaluated as “Normal”, “Abnormal, not clinically significant”, or “Abnormal, clinically significant”. The physical examination results of each scheduled visit will be summarized per treatment group and overall profile, for which the number of cases and percentage under each category of the results will be calculated and cross tabulations will be formulated. The abnormal records will be listed.

3.5 Analysis of Other Endpoints

3.5.1 Study Product Defects

The study product defects will be tabulated.

4 Interim Analysis and Data Monitoring Committee (DMC)

Based on the feedback from the investigator that the target incision adhesion rate observed during the phase 2 operation (ileostomy reversal) is very low, an interim analysis will be added. The interim analysis will be performed after at least 94 subjects (accounting for at least 61% of the total subjects) have completed the primary endpoint evaluation.

The timeline for the interim analysis is September 15, 2020.

The interim analysis will include the following subjects:

- a) All subjects that have undergone the phase 2 operation,
- b) Subjects who withdrew from the study without undergoing the phase 2 operation;
- c) Subjects who have neither undergone the phase 2 operation nor withdrawn from the study, but have undergone the phase 1 operation before or on September 15, 2019.

The conditional power (CP) is the probability that the final result will be significant, given the data observed as of the interim analysis. The equation for calculating the CP is as follows:

$$P_{lk}(\theta) = \Phi \left(\frac{-Z_k \sqrt{I_k} - z_{1-\alpha} \sqrt{I_k} - \theta(I_K - I_k)}{\sqrt{I_K - I_k}} \right)$$

Where,

$Z_k = \frac{p_{2k} - p_{1k}}{\sqrt{\sigma^2 \left(\frac{1}{n_{1k}} + \frac{1}{n_{2k}} \right)}}$; p_{2k} and p_{1k} are the adhesion rates of the experimental group and control group at the time of the interim analysis, while n_{2k} and n_{1k} are the numbers of subjects with evaluable primary endpoint in the experimental group and control group at the time of the interim analysis.

$$I_k = \frac{1}{\sigma^2} \left(\frac{1}{n_{1k}} + \frac{1}{n_{2k}} \right)^{-1}$$

$I_K = \frac{1}{\sigma^2} \left(\frac{1}{n_1} + \frac{1}{n_2} \right)^{-1}$, n is the total number of subjects in the experimental group and control group, and in this study, $n_1 = n_2 = 77$;

$\sigma^2 = \bar{p}(1 - \bar{p})$, $\bar{p} = (P_1 + P_2)/2$, P_2 and P_1 are the expected adhesion rates of the experimental group and control group, and in this study, $P_2 = 0.5$, $P_1 = 0.75$;

$$\Theta = P_2 - P_1;$$

$$Z_{1-\alpha} = Z_{1-0.025} = 1.96 \text{ (one-sided 97.5% critical Z-value);}$$

Φ : Area under the standard normal distribution curve

[Table4](#) provides the CP for various adhesion rate differences between INTERCEED group and control group at the time of the interim analysis. Given an anticipated dropout rate of 30%, it is planned that there will be a total of 154 subjects with evaluable primary endpoint (77 in each group) by the time the study is completed. The interim analysis will be performed after at least 94 subjects (accounting for at least 61% of the total subjects) have completed the primary endpoint evaluation. If $CP \leq 60\%$, the observed target incision adhesion rate difference between the two groups is only 0.10 or so, which is much smaller than the assumed difference of 0.25 used in the sample size calculation. Accordingly, the study will be terminated due to the low adhesion rate and the small effect size between INTERCEED group and control group. Otherwise, the study will continue until it is completed as originally planned.

Database lock will be performed for the interim analysis. All data provided for analysis will be cleaned through 100% source data verification. Statistical analyses will be performed according to the updated and approved protocol and SAP to determine whether the interim results meet the predefined threshold for early discontinuation ($CP \leq 60\%$).

Table4 Conditional Power for the Effect Size between Treatment Groups Observed during the Interim Analysis

Adhesion Rate Difference between Treatment Groups Observed at the Interim Analysis	Available Data at Interim Analysis Percentage of Subjects with Evaluable Primary Endpoint (Number of Subjects)				
	61% (94)	66% (102)	70% (108)	72% (112)	75% (116)
-0.02	0.19	0.11	0.07	0.04	0.02
-0.06	0.35	0.26	0.2	0.16	0.12
-0.08	0.45	0.37	0.3	0.26	0.21
-0.1	0.55	0.48	0.42	0.38	0.34
-0.11	0.59	0.54	0.49	0.45	0.41
-0.12	0.64	0.6	0.56	0.52	0.49
-0.13	0.69	0.65	0.62	0.6	0.57
-0.14	0.73	0.7	0.68	0.66	0.64
-0.15	0.77	0.75	0.74	0.72	0.71
-0.16	0.81	0.8	0.79	0.78	0.78
-0.18	0.87	0.87	0.87	0.87	0.87

5 Modifications to the Original Analysis Plan

Not applicable.

6 References

1. Sekiba K. Use of Interceed(TC7) absorbable adhesion barrier to reduce postoperative adhesion reformation in infertility and endometriosis surgery. The Obstetrics and Gynecology Adhesion Prevention Committee. Obstet Gynecol. 1992 Apr;79(4):518-22.

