## 8.6. Criteria and Reason for Terminating the Trial based on the Statistical Results

An ad-hoc interim analysis is proposed based on feedback received from the investigators who observed very low rate of adhesions at the second procedure for ostomy reversal.

The conditional power (CP) is the probability that the final result will be significant, given the data obtained up to the time of interim look. The table as below shows the CP per different adhesion rate difference of INTERCEED vs Control arms at the interim look.

Given the assumed 30% drop-out rate, it was planned that a total of 154 participants (77 per arm) with evaluable primary endpoint are available by the study completion. The interim analysis will be performed while at least 94 participants (at least 61% of the total number) have their primary endpoints evaluated in the electronic data collection system. If the CP is  $\leq 60\%$ , the observed adhesion rate difference magnitude between two arms is only around 0.10, which is much less than the assumed difference magnitude of 0.25 used for sample size calculation. Therefore, the study will be terminated due to low adhesion rate and small effect size between INTERCEED and control arms. Otherwise, the study will continue until the study completion as planned.

There is a database lock for this interim analysis. All data for the analysis will be cleaned with 100% source data validation. The statistical analysis will be conducted per updated and approved protocol and SAP to determine if the interim results meet the pre-specified threshold of early discontinuation ( $CP \leq 60\%$ ).

Table: Conditional power per different treatment effect size observed at interim look

Observed adhesion difference between INTERCEED vs control at interim look	Data availability at interim look				
	Percentage of participants with evaluable primary endpoint (number of participants)				
	61% (94)	66% (102)	70% (108)	72% (112)	75% (116)
-0.02	0.19	0.11	0.07	0.04	0.02
-0.06	0.35	0.26	0.2	0.16	0.12
-0.08	0.45	0.37	0.3	0.26	0.21
-0.1	0.55	0.48	0.42	0.38	0.34
-0.11	0.59	0.54	0.49	0.45	0.41
-0.12	0.64	0.6	0.56	0.52	0.49
-0.13	0.69	0.65	0.62	0.6	0.57
-0.14	0.73	0.7	0.68	0.66	0.64
-0.15	0.77	0.75	0.74	0.72	0.71

-0.16	0.81	0.8	0.79	0.78	0.78
-0.18	0.87	0.87	0.87	0.87	0.87

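### As supplied, the SAP's conditional-power equation does not generate Table 4: its critical-value term uses interim instead of final information, which moves the stopping cut-off towards continuing

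*SAP*

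**What the plan says.** SAP section 4 defines conditional power (CP) as the chance that the final result will be significant given the interim data, and stops the trial if CP is 60% or less. It introduces the formula with "The equation for calculating the CP is as follows". The numerator of that equation reads, in the text supplied, "Z_k \sqrt{I_k} - z_{1-\alpha} \sqrt{I_k} - \theta(I_K - I_k", with a minus sign in front. The section defines I_k (information at the interim look) and I_K (information at the end, 77 per arm) separately, and gives 1.96 as the "one-sided 97.5% critical Z-value".

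The other inputs are explicit. For the variance and the effect, "P_2 and P_1 are the expected adhesion rates of the experimental group and control group", set at 0.5 and 0.75. For the final size, "it is planned that there will be a total of 154 subjects with evaluable primary endpoint (77 in each group"). For timing, "The interim analysis will be performed after at least 94 subjects" have the primary endpoint evaluated.

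Table 4 lists CP for 11 observed differences at 94, 102, 108, 112 and 116 subjects. Protocol 8.6 carries the same table but no equation. Both documents translate the threshold into a difference: "the observed target incision adhesion rate difference between the two groups is only 0.10 or so" (SAP) and "the observed adhesion rate difference magnitude between two arms is only around 0.10" (Protocol 8.6).

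**The concern.** If the final test is made at 1.96, the critical-value term in a CP formula must be scaled by the final information, I_K. Scaling it by I_k tests the final data against a lower hurdle and inflates CP.

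This matters because CP is the trial's only statistical stopping rule and the SAP holds the only equation for it. Real interim data will seldom fall on a tabulated difference and sample size, or split equally between arms, so whoever programs the analysis will need the equation. If it disagrees with the table, the plan contains two stopping rules. Finding that out once unblinded results are in hand would leave a choice between them that prespecification is meant to prevent.

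**Working it through.** **Inputs (SAP section 4).** Expected adhesion rates 0.50 and 0.75, so theta = -0.25 and the mean rate is 0.625; sigma² = 0.625 × 0.375 = 0.2344; z = 1.96; 77 per arm at the end. I assume equal arms at the interim (47 per arm at 94 subjects). With d the observed difference (INTERCEED minus control), Z_k√I_k = d × I_k.

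**Information at 94 subjects.** I_k = 47/(2 × 0.2344) = 100.3, root 10.01. I_K = 77/(2 × 0.2344) = 164.3, root 12.82. I_K - I_k = 64.0, root 8.0.

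**One cell, d = -0.10 at 94 subjects (Table 4: 0.55).**
- With √I_K in the z term: (10.03 - 1.96 × 12.82 + 16.0)/8.0 = 0.11, CP = 0.545. This is the table's figure.
- With √I_k as supplied: (10.03 - 1.96 × 10.01 + 16.0)/8.0 = 0.80, CP = 0.788.

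**All 55 cells.**
- With √I_K: 55 of 55 agree to the two decimals shown; the largest gap, 0.005, is rounding.
- With √I_k: 0 of 55 agree; gaps run from 0.054 to 0.27.
- Other readings fail too. The number of cells within 0.02 of the table is 1 for the current-trend effect with I_K and 9 with I_k, 6 for an unpooled variance with I_K and 0 with I_k, 0 for 110 per arm at the end, and 0 for z = 1.645 with I_k.

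**Implied final hurdle.** The supplied term equals a final critical value of 1.96 × √(94/154) = 1.53 at 94 subjects (one-sided level about 0.063). At 116 subjects it is 1.96 × √(116/154) = 1.70.

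**Difference at which CP = 60%.** Setting the bracket to 0.253 and solving, at 94 subjects:
- √I_K: (0.253 × 8.0 + 25.12 - 16.0)/100.3 = 0.111
- √I_k: (0.253 × 8.0 + 19.63 - 16.0)/100.3 = 0.056

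| Subjects | Cut-off with √I_K (Table 4) | Cut-off with √I_k (supplied) | Reduction in size |
|---|---|---|---|
| 94 | -0.111 | -0.056 | 49% |
| 102 | -0.121 | -0.078 | 36% |
| 108 | -0.127 | -0.092 | 28% |
| 112 | -0.131 | -0.100 | 24% |
| 116 | -0.134 | -0.107 | 20% |

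**Decisions.** In 18 of the 55 cells the two versions fall on opposite sides of 60%. In all 18 the table stops and the supplied equation continues. Examples (table against equation): -0.10 at 94 subjects, 0.55 and 0.79; -0.11 at 108, 0.49 and 0.71; -0.13 at 116, 0.57 and 0.76.

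**The case against.** The strongest answer is that the SAP may not contain this error. The point turns on one letter's case inside a typeset equation that a program read from PDF. Case is loose elsewhere in that section: theta and z are lower case in the equation and capitals in the definitions. That all 55 cells match with I_K shows that the authors calculated with I_K, which fits a correct equation with one misread capital as well as it fits a drafting slip. The same line does keep I_K and I_k apart in two other places, which makes a misreading less likely but does not exclude it. This objection stands as a condition: the source must be checked.

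It is also fair that the intended rule can be recovered. The table, the definition of CP and the stated 1.96 all point to I_K, and a statistician testing a program against Table 4 would see the mismatch at once. That limits the harm but does not make the equation usable as supplied.

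On the 0.10 remark, both documents word it as an approximation and it does not define the rule. It is reasonable at 94 subjects, where the boundary is 0.111, and the drift at larger sizes can be read from the adjacent table. So it is a secondary matter.

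A reader might infer three stronger things that the documents do not support:
- That the printed form halves the cut-off wherever the look falls. This holds only at 94 subjects, the minimum and the extreme case. The band of conflicting decisions narrows from about 0.055 wide at 94 (0.111 - 0.056) to about 0.027 at 116 (0.134 - 0.107).
- That Table 4 or the 60% threshold is wrong. The table follows exactly from the stated inputs.
- That the final test would run at a level of about 0.063. The 1.53 arises only inside the CP calculation; the final analysis in SAP 3.3.1 still rests on a two-sided 95% interval.

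**Conclusion.** The concern holds for the text as supplied, subject to a check of the subscript in the source PDF. The equation behind the only statistical stopping rule uses interim information where final information is needed and contradicts the SAP's own table in every cell. The error runs one way, towards continuing a trial that the table would stop. If the source shows I_K, this part of the point falls away.

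The cut-offs assume equal interim arms and the SAP's fixed variance and effect. Independently of the subscript, describing the threshold as a difference near 0.10 understates the boundary as the look moves beyond 94 subjects, up to 0.134 at 116.

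**What to change.** 1. Check the subscript in the z term of the CP equation in the source PDF of the SAP. If it is I_k, replace it by I_K, so that the equation generates Table 4. Leave Table 4, the 60% threshold and the other inputs unchanged.
2. In SAP section 4 and Protocol 8.6, replace the figure of about 0.10 by about 0.11 at 94 subjects rising to about 0.13 at 116 (equal arms), or refer to the table. This is worth doing whatever the subscript check shows. The Protocol synopsis does not give the 0.10 figure and needs no change.

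The cost is one symbol and one sentence in the SAP and one sentence in the protocol, with no effect on design, sample size or data collection. A confirmed subscript error should be corrected before the interim analysis is run.

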7.1 Four Abdominal Quadrants (Figure)
